7.1.1 Randomization and Blinding

This study will be double blinded with regard to the dose intensification strategy and with regard to route of administration. All patients will receive both intermittent Q12 bolus and

continuous IV infusion, one of which will contain furosemide and one of which will contain normal saline ("double-dummy" design).

7.2 48 to 72 hours

At 48 hours, the treating physician will choose one of the following options based on the clinical assessment of the patient and their response to therapy:

- 1. Maintain current strategy without change
- 2. Increase dose by 50% (while remaining blinded)
- 3. Change to oral diuretics (dose at MD discretion) in preparation for discharge

7.3 72 hours and afterwards

After 72 hours, all patient care decisions including diuretic dose and administration will be unblinded and at the discretion of the investigator.

7.4 Study Drug Supplies

Investigational pharmacy will prepare both intermittent bolus (furosemide or placebo) and continuous infusion (furosemide or placebo) for each patient in keeping with the "double dummy" study design. Hospital stock should be used. Clinical personnel, investigators, and the patients will be blinded to both dose intensification strategy and route of administration.

7.5 Patient Safety, Concomitant Therapies, and Rescue Therapy

This study will evaluate and compare initial diuretic strategies in patients with acute heart failure and volume overload. Although investigators are encouraged to follow the assigned treatment strategy for the duration of the treatment period (72 hours), in all cases the patient's safety based on the clinical judgment of the treating physician will take priority over the specific treatment assignment.

Patients requiring other intravenous vasoactive medications for heart failure (inotropes, vasodilators, etc) will be excluded from the present study. Patients requiring such drugs for clinical reasons during the randomization period will meet the secondary endpoints of "worsening or persistent heart failure" and "treatment failure" (see endpoint section). Patients who are deemed to have a clinical need for additional diuretics during the blinded study period will be permitted to receive unblinded open label diuretics. This will be captured as "rescue therapy" and will meet criteria for secondary endpoints of "worsening or persistent heart failure" and "treatment failure" endpoints. Conversely, patients may develop signs or symptoms of over-diuresis (such as hypotension) that necessitate holding or discontinuing diuretics before completion of the randomization period. This will be captured as a "treatment failure" if it requires specific intervention beyond simply holding diuretics.

As this is a randomized trial comparing initial diuretic strategies, in either case the interpretation of the primary endpoints with regard to both efficacy and renal function will be on an "intention to treat" basis.

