5. BASIC STUDY DESIGN

This study will be a randomized, controlled, multi-center clinical trial of patients with signs and symptoms consistent with AHF within 24 hours of hospital admission. A total of 300 patients will be enrolled in the trial.

Patients will be randomized to one of 4 treatment regimens (75 patients / treatment regime) defined by a 2x2 factorial treatment design:

1) "High intensification" strategy for IV furosemide (defined as 2.5 x stable PO home dose) vs. "low intensification" dose IV furosemide (defined as 1 x stable PO home dose). This treatment will be double-blinded.

2) Continuous furosemide IV infusion vs. IV furosemide given as IV bolus Q12 hours. This treatment will be double-blinded.

The study treatment regimen will be administered from randomization through 48 hours, at which point the investigator may modify the IV loop diuretic strategy based on clinical assessment of the patient and their response to therapy. Permitted modifications will be:

- 1. Continue current strategy without change
- 2. Increase dose by 50% (while remaining blinded to both dose and route of administration assignment)
- 3. Switch to oral furosemide (dose at the investigator's discretion) in preparation for discharge.

Blinding of initial treatment assignment will be maintained regardless of which of the options are selected.

After 72 hours, all diuretic treatment will be open label at the treating physician's discretion.

The primary assessment for both efficacy and safety will occur at 72 hours after randomization.

The primary endpoint for efficacy will be patient reported global well being by visual analog scale (VAS) quantified as the area under the curve (AUC) over 72 hours.

The primary safety endpoint will be change in serum creatinine from baseline to 72 hours.

Anticipated need for at least 48 hours of IV diuretic therapy will be an inclusion criterion for the study. However, if patients are deemed to have achieved adequate diuresis before 48 hours, they may be switched to oral dosing of diuretics (open label) at the investigators discretion. If patients are discharged prior to 72 hour assessment, the last VAS

DOSE protocol version 18.1; February 4, 2008

assessment and last serum creatinine will be carried forward to 72 hours for the purposes of assessing the primary endpoints.

If patients die prior to 72 hour assessment, the last serum creatinine will be carried forward and the last VAS will be imputed as 0.

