6.2 Exclusion Criteria

- BNP < 250 ng/ml or NT-proBNP <1000 mg/ml
- Received IV vasoactive treatment or ultra-filtration therapy for heart failure since initial presentation
- Anticipated need for IV vasoactive treatment or ultra-filtration for heart failure during this hospitalization
- Substantial diuretic response to pre-randomization diuretic dosing such that higher doses of diuretics would be contra-indicated (based on investigator judgment)
- Systolic BP <90 mmHg
- Serum creatinine >3.0 mg/dl at baseline or renal replacement therapy
- Hemodynamically significant arrhythmias
- Acute coronary syndrome within 4 weeks
- Active myocarditis
- Hypertrophic obstructive cardiomyopathy
- Severe stenotic valvular disease
- Restrictive or constrictive cardiomyopathy
- Complex congenital heart disease
- Constrictive pericarditis

- Non-cardiac pulmonary edema;
- Clinical evidence of digoxin toxicity;
- Need for mechanical hemodynamic support
- Sepsis
- Terminal illness (other than HF) with expected survival of less than 1 year
- Previous adverse reaction to the study drugs
- Use of IV iodinated radiocontrast material in last 72 hours or planned during hospitalization
- Enrollment or planned enrollment in another randomized clinical trial during this hospitalization
- Inability to comply with planned study procedures

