11. OUTCOME DETERMINATIONS

11.1 **Primary Endpoints**

This study will use co-primary endpoints

• Change in serum creatinine from randomization to 72 hours

• Area under the Curve (AUC) for Patient Global Assessment by VAS over 72 hours

Rationale for Primary Endpoints:

Change in creatinine from randomization to 72 hours was chosen as the primary safety endpoint due to the observed association between diuretic dosage and worsening renal function and the known association of worsening renal function with other adverse outcomes.

For the assessment of short term efficacy, a variety of endpoints have been utilized in prior AHF studies. These include patient self assessments of symptoms, typically either dyspnea or global well being (termed patient global assessment (PGA)). These self assessments are usually performed using a visual analog scale (VAS) or Likert scale. The DOSE-AHF study will use the PGA by VAS over 72 hours as the primary endpoint for efficacy. The rationale for this choice is that although dyspnea is the primary symptom for most patients with AHF, other symptoms (fatigue, edema, etc) may also be important and should be captured in the primary efficacy endpoint. We have chosen a patient symptom assessment r ather than other measures of diuretic efficacy such as weight change or urine output, because while these measures capture the pharmacodynamic effects of diuretic therapy, they may not be tightly correlated with other clinical events (such as rehospitalization or death), and are therefore not ideal surrogates in the assessment of efficacy.

Patients will be asked to self assess both their general well being and their level of dyspnea using a visual analog scale (VAS) method. For PGA, patients will mark their global well being on a 10 cm vertical line, with the top labeled "best you have ever felt" and the bottom labeled "worst you have ever felt". For dyspnea, the labels will be "I am not breathless at all" and "I am as breathless I have ever been". The VAS is scored from 0 to 100 but the patient is unaware of the numerical value of their response. Patients will self assess both PGA and dyspnea at randomization, 6, 12, 24, 48, 72, and 96 hours. The area under the curve for PGA assessment over the first 72 hours will be the primary efficacy endpoint (AUC for PGA VAS).

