11.2 Secondary Endpoints

- *Weight Loss:* Weight loss will be measured over the 96 hour study period (at 24, 48, 72, and 96 hours from randomization).
- **Proportion of Patients Free of Congestion at 72 hours:** Freedom from congestion will be defined as JVP < 8 cm, no orthopnea, trace peripheral edema or less
- Change in the bivariate relationship of creatinine at 72 hours vs. weight loss at 72 hours: For each of the four treatment groups, weight loss at 72 hours and change in creatinine at 72 hours will be plotted on a two dimensional coordinate grid along with estimates of the mean effect and a 95% confidence ellipse. This will allow visual and statistical assessment of the "trade off" between change in weight and change in renal function. Comparisons among the 6

possible pairwise treatment differences will be constructed to detect differences between treatment strategies.

- Differences in Dyspnea VAS AUC over 24, 48, and 72 hours
- Differences in PGA VAS AUC over 24 and 48 hours
- Change in Serum Creatinine from baseline to 24, 48, 96 hours, day 7/discharge, and 60 days
- Change in Cystatin C from baseline to 72 hours, Day 7/discharge, and 60 days
- Worsening or persistent heart failure: defined as need for rescue therapy (additional open label loop diuretic, addition of thiazide, IV vasoactive agent for heart failure treatment, ultrafiltration, mechanical circulatory or respiratory support) over 72 hours after randomization
- **Development of Cardio-renal syndrome:** defined as increase in serum creatinine > 0.3 mg/dl from randomization at any time point during 72 hours after randomization
- **Treatment Failures**, a composite comprised of ANY ONE of the following during the 72 hours after randomization:
 - o development of cardio-renal syndrome as defined above
 - worsening/persistent heart failure as defined above
 - clinical evidence of over-diuresis requiring intervention (such as administration of IV fluids)
 - o death
- Net fluid loss over study period: Assessed at 24, 48, and 72 hours
- Time from randomization to discharge during index hospitalization
- Total days hospitalized for heart failure or deceased during the 60 days after randomization
- Changes in circulating biomarkers at 72 hours, day 7 (or discharge) and 60 days
- Death or rehospitalization (to include unscheduled clinic visits or ED visits) at 60 days

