14.2 Analysis of Primary Endpoints

The primary analysis will be made on an intention-to-treat basis, with patients allocated to the treatment to which randomized. General linear models will be used to examine the effect of each of the main effects on the two co-primary outcomes. The dependent variables in the regression model will be the change in creatinine value from baseline to 72 hours and the AUC for the PGA VAS from baseline through 72 hours. Independent variables in the model will include the main effects of furosemide dose and mode of administration, and the baseline creatinine level. An interaction term will be included if the p-value for that parameter estimate is less than 0.025. For each co-primary outcome, the two main effects will be that the treatment (either dose or mode of administration) has no effect on either of the co-primary outcomes.

We anticipate that some patients may die before all scheduled post-baseline creatinine values can be taken, and that these losses will introduce bias into the main effects comparisons. For the primary analyses, the values imputed will be 0 for the PGA VAS after the time of death and the highest post-baseline creatinine measurement. Sensitivity analyses, including analysis of only complete cases and imputing the worst creatinine value for deaths, will be employed to assess the degree to which these missing values impact the results.

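### A creatinine lowered by dialysis or haemofiltration before 72 hours enters the co-primary safety analysis by default, where it can understate renal harm

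*Protocol*

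**What the plan says.** Section 11.1 of the protocol defines the co-primary safety endpoint as "Change in serum creatinine from randomization to 72 hours". Section 14.2 puts that quantity into the model: "The dependent variables in the regression model will be the change in creatinine value from baseline to 72 hours". Patients are analysed as randomized. Section 7.5, after describing rescue therapy and over-diuresis, adds that "in either case the interpretation of the primary endpoints with regard to both efficacy and renal function will be on an" intention-to-treat basis.

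The protocol replaces a creatinine value in two situations only:

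- **Death before 72 hours.** Section 5 says "If patients die prior to 72 hour assessment, the last serum creatinine will be carried forward and the last VAS will be imputed as 0". Section 14.2 says "the values imputed will be 0 for the PGA VAS after the time of death and the highest post-baseline creatinine measurement".
- **Discharge before 72 hours.** The last VAS "assessment and last serum creatinine will be carried forward to 72 hours for the purposes of assessing the primary endpoints" (Section 5).

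Renal replacement therapy is mentioned once, as a baseline exclusion: "Serum creatinine >3.0 mg/dl at baseline or renal replacement therapy" (Section 6.2). Among the secondary endpoints in Section 11.2, rescue therapy includes additional open-label loop diuretic and also "addition of thiazide, IV vasoactive agent for heart failure treatment, ultrafiltration, mechanical circulatory or respiratory support". Treatment failure comprises cardio-renal syndrome, worsening or persistent heart failure, over-diuresis needing intervention, and death. Renal replacement for renal failure is not named in either list.

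**The concern.** The safety hypotheses in Sections 2.1 and 2.2 ask which strategy causes less renal dysfunction. Dialysis and haemofiltration remove creatinine from the blood, so a value drawn after either has started no longer measures that. The patients affected are those whose kidneys did worst. Under the stated rules their 72-hour value is used as measured, and the recorded change is smaller than the renal injury, or negative if the value has dropped below baseline.

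The event is foreseeable from the protocol itself. Section 4.2 describes a small study stopped early for more renal impairment and renal failure in its high-dose furosemide arms, and Section 6.2 admits patients with creatinine up to 3.0 mg/dl. If cases gather in the arm that harms the kidney more, the analysis is pulled away from detecting that harm.

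**Working it through.** **1. Which value is used after which event**

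| Event before 72 hours | Creatinine used | Source |
|---|---|---|
| Death | Last value, or highest post-baseline value | Section 5, or Section 14.2 |
| Discharge | Last value | Section 5 |
| Rescue therapy, over-diuresis | As measured, intention to treat | Section 7.5 |
| Dialysis or haemofiltration | No rule, so as measured | Section 14.2 by default |

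The last row follows from the general rule in 14.2 and the absence of an exception. The result is inconsistent. Under 14.2, a dialysed patient who then dies is scored with the pre-dialysis peak if that is the highest post-baseline value. One with the same renal course who survives is scored with the lowered value.

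**2. The plan's own power figure**

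Inputs from Section 14.3: 150 patients per level of each factor, difference 0.20 mg/dL, SD 0.5 mg/dL, two-sided alpha 0.025.

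- Standard error = 0.5 × √(2/150) = 0.0577
- 0.20 / 0.0577 = 3.464; critical value 2.241
- Power = Φ(3.464 − 2.241) = Φ(1.223) = 88.9% (88.6% by noncentral t), against a stated 88%
- At SD 0.4: 98.2%, against a stated 98%

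The design inputs reproduce, so 0.20 mg/dL is a fair yardstick.

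**3. One patient (assumed values)**

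- Baseline 2.5, peak 4.0 before dialysis, 2.0 at 72 hours. Recorded change 2.0 − 2.5 = −0.5; change to the peak 4.0 − 2.5 = +1.5. Understatement 1.5 − (−0.5) = 2.0 mg/dL, with apparent improvement.
- Baseline 1.5, 2.5 at 72 hours after dialysis. Recorded change +1.0, still scored as harm, though less than the true rise if the peak was above 2.5.

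**4. Effect on the comparison**

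Shift in the mean difference = (excess patients in one arm / 150) × understatement per patient. For one excess patient at 2.0 mg/dL: 2.0/150 = 0.0133 mg/dL, and 0.0133/0.20 = 6.7%.

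Neither the number of cases nor the lowering is in the protocol, so both are assumed. Each cell gives the shift in mg/dL, its share of 0.20, and the power if a true difference of 0.20 is reduced by that shift with the SD held at 0.5.

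| Excess patients | 1 mg/dL each | 2 mg/dL each | 3 mg/dL each |
|---|---|---|---|
| 1 | 0.007; 3%; 86.6% | 0.013; 7%; 83.9% | 0.020; 10%; 81.0% |
| 2 | 0.013; 7%; 83.9% | 0.027; 13%; 77.7% | 0.040; 20%; 70.2% |
| 3 | 0.020; 10%; 81.0% | 0.040; 20%; 70.2% | 0.060; 30%; 57.3% |
| 5 | 0.033; 17%; 74.1% | 0.067; 33%; 52.7% | 0.100; 50%; 30.5% |

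The power figures apply when the excess lies in the arm with more renal harm. An excess in the other arm would enlarge the difference by the same amount. With equal numbers and equal lowering in both arms the shift is zero.

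**The case against.** The strongest reply is that this is silence, not error. The handling of laboratory values after dialysis is often left to the SAP, which is not at hand, and analysing measured values whatever therapy follows is a recognised intention-to-treat choice. Part of this stands: an SAP could supply the rule. But the protocol does not leave creatinine substitution to a later document. It sets rules for death and for early discharge, and its default for everything else is the measured value. The omission falls on the event closest to the endpoint.

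Four stronger readings are tempting and are not supported:

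- **That Section 7.5 expressly keeps post-dialysis values.** Its sentence refers back to rescue therapy and over-diuresis; dialysis is not mentioned. The default comes from the general rule in 14.2.
- **That such a patient is always scored as improved.** That needs a 72-hour value below baseline. Otherwise the rise is understated but still counts as a rise.
- **That a patient dialysed between the scheduled draws escapes the cardio-renal criterion.** Section 11.2 counts a rise above 0.3 mg/dl at any time point within 72 hours and does not limit this to scheduled samples. A pre-dialysis value can trigger it, and through it treatment failure.
- **That a large part of the design difference is at risk.** The lower rows of the table need several cases, all in excess on one side, within 72 hours, in patients whose entry creatinine was capped at 3.0 mg/dl. Nothing in the protocol says that this will occur, and such cases are probably rare.

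Other safeguards exist: creatinine at other times, cystatin C at 72 hours, and ultrafiltration counted as rescue. They are secondary and do not correct the co-primary value. Adverse event reporting is a weak backstop, since Section 13.2.1 exempts acute renal failure from the adverse event form.

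**Conclusion.** The point holds as a gap with a foreseeable direction for the individual patient: following the stated rules, a creatinine lowered by dialysis or haemofiltration enters the co-primary safety analysis and can understate renal harm. Whether it biases the comparison depends on an excess of such cases in one arm. The size is unknown. Assuming 2.0 mg/dL of understatement, each excess patient is worth about 0.013 mg/dL, or 7% of 0.20 mg/dL. One case is minor; a small cluster in one arm would matter. The amendment is worth making because it is cheap and protects the primary safety question, not because the protocol shows that serious bias is likely.

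**What to change.** In Section 14.2, with a cross-reference in 7.5, state that:

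- creatinine values after the start of dialysis or haemofiltration are not used for the 72-hour change;
- the highest creatinine from randomization to the start of that therapy is used instead, including unscheduled local values, in line with the 14.2 rule for deaths;
- an analysis of the raw measured values is reported as a sensitivity analysis.

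In Section 11.2, name renal replacement started for renal failure within 72 hours as a component of treatment failure. Leave the 0.3 mg/dl definition of cardio-renal syndrome unchanged, so that patients treated for volume without a creatinine rise are not relabelled.

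Because the new rule borrows from the rule for deaths, Sections 5 and 14.2 must be reconciled at the same time: one carries forward the last creatinine, the other takes the highest post-baseline value.

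The cost is a few sentences and one CRF field: date and time of first renal replacement, with the last creatinine before it. No study procedure is added. The creatinine distribution becomes slightly more skewed. In the assumed example, a change of +1.5 in one of 300 patients, taking the mean change as near zero, adds about 1.5²/300 = 0.0075 to a variance of 0.25, so the SD rises from 0.500 to about 0.507. The standardised difference is then 0.20/0.507 = 0.39, against (0.20 − 0.0133)/0.50 = 0.37 if the lowered value is kept, so in that example the wider spread costs less than the understatement.

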8. RECRUITMENT AND SCREENING PROCEDURES

8.1 Common Recruitment/Screening Procedures

All patients admitted to the participating Heart Failure Clinical Research Network centers with signs and symptoms suggestive of AHF will be screened by a study coordinator. Given the short time period after admission (24 hours) for inclusion in the study, it is anticipated that screening in the Emergency Department and screening more than once daily will be effective recruitment strategies. Patients meeting eligibility criteria will be approached regarding participation in this study.

8.2 Estimated Enrollment Period

This study will enroll 300 patients at 9 Regional Clinical Centers (RCCs) and associated satellite centers in the United States and Canada. It is projected that 18 patients per month will be enrolled (2 pts/RCC/month), for a total anticipated enrollment period of approximately 18 months.

8.3 Informed Consent Procedures

8.3.1 Informed Consent

All patients will have the purpose of the study, the study interventions and evaluations, and the potential risks and benefits of participation explained to them and their questions answered. If they consent to participation in this study, they will review and sign the informed consent form (ICF). A template for the ICF appears in Appendix D.

8.3.2 Confidentiality and HIPAA Requirements

All information collected on study participants will be stored in a confidential manner using procedures in place at each participating RCC. Only approved study personnel will have access to data collected as part of the DOSE Study. Study participants will be identified by a Subject ID # on all study documents. Data will be transmitted to the DCC in a secure manner, and stored securely at the DCC using standard DCRI operating procedures.

